3.6.3 Clinical Laboratory Tests

The number and percentage of patients with the following abnormalities will be presented:

- ALT $\geq 3 \times \text{ULN}$, $\geq 5 \times \text{ULN}$, $\geq 10 \times \text{ULN}$, and $\geq 20 \times \text{ULN}$
- AST $\geq 3 \times \text{ULN}$, $\geq 5 \times \text{ULN}$, $\geq 10 \times \text{ULN}$, and $\geq 20 \times \text{ULN}$
- Total bilirubin $\geq 2 \times \text{ULN}$
- Potential Hy's Law cases: ALT or AST $> 3 \times \text{ULN}$, total bilirubin $\geq 2 \times \text{ULN}$, and ALP $< 2 \times \text{ULN}$ at the same visit

Selected clinical laboratory evaluations (i.e., chemistry and hematology) may be summarized using descriptive statistics or CTCAE grade shift tables as appropriate.

All local laboratory assessments, including chemistry, coagulation, hematology, thyroid function will be listed by patient. Applicable chemistry (Alanine Aminotransferase, Albumin, Alkaline Phosphatase, Amylase, Aspartate Aminotransferase, Bilirubin, Creatinine, Glucose, Lactate Dehydrogenase, Lipase, Potassium, Sodium), and hematology (Eosinophils, Hemoglobin, Leukocytes, Lymphocytes, Neutrophils, Platelets) parameters will be graded according CTCAE v5.0. For some laboratory tests, the CTCAE criteria may include qualifying definitions (e.g., clinical AE and/or requirement for concomitant medication) in addition to the specific laboratory value used for the definition of the toxicity grades. For such tests, the qualifying definitions will not be used for the assignment of toxicity grades.

3.6.4 Vital Signs

Descriptive statistics will be provided for vital signs measurements (systolic and diastolic blood pressure, heart rate, body temperature, and weight) and oxygen saturation measurements, in which absolute values and changes from baseline for the minimum, maximum, and last post-baseline values will be presented. Both scheduled and unscheduled post-treatment values will be considered for summaries of the minimum, maximum, and last post-baseline values.

The number and proportion of subjects with potentially clinically significant changes in vital signs will be presented based on the following thresholds:

- Systolic blood pressure ≥ 160 mmHg and increase ≥ 20 mmHg from baseline
- Systolic blood pressure ≤ 90 mmHg and decrease ≥ 20 mmHg from baseline
- Diastolic blood pressure ≥ 100 mmHg and increase ≥ 15 mmHg from baseline
- Systolic blood pressure ≤ 50 mmHg and decrease ≥ 15 mmHg from baseline
- Heart rate ≥ 120 bpm with increase ≥ 15 bpm from baseline
- Heart rate ≤ 50 bpm with decrease ≥ 15 bpm from baseline

All vital signs data will be listed by patient.

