10.6.9 Other Safety Data

Vital signs, body weight, and ECOG performance status data will be summarized descriptively by visit and/or with shift tables. Summaries of clinically notable measurements may also be provided. Definitions of “clinically notable” will be provided in the SAP.

A more detailed description of study analyses will be presented in the SAP.

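### The fourth blood-pressure threshold in SAP 3.6.4 names systolic pressure where diastolic is evidently meant, so the table defines no low-diastolic count

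*SAP*

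**What the plan says.** SAP 3.6.4 commits to a threshold table: "The number and proportion of subjects with potentially clinically significant changes in vital signs will be presented based on the following thresholds". Six rows follow. The four blood-pressure rows are, in order:

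1. "Systolic blood pressure ≥ 160 mmHg and increase ≥ 20 mmHg from baseline"
2. "Systolic blood pressure ≤ 90 mmHg and decrease ≥ 20 mmHg from baseline"
3. "Diastolic blood pressure ≥ 100 mmHg and increase ≥ 15 mmHg from baseline"
4. "Systolic blood pressure ≤ 50 mmHg and decrease ≥ 15 mmHg from baseline"

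The last two rows give a high and a low limit for heart rate.

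The same section provides two other displays. One is a numerical summary: "Descriptive statistics will be provided for vital signs measurements (systolic and diastolic blood pressure, heart rate, body temperature, and weight". It covers absolute values and changes from baseline for the minimum, maximum and last post-baseline readings, and it includes unscheduled readings. The other is a listing: "All vital signs data will be listed by patient".

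The protocol sets no on-study limits of its own for this purpose. Protocol 10.6.9 hands the task over: "Definitions of “clinically notable” will be provided in the SAP".

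**The concern.** The list appears to be built in pairs, high then low, for systolic pressure, diastolic pressure and heart rate. The row where the low-diastolic limit belongs is labelled systolic. Since the protocol leaves these definitions to the SAP, and neither document gives a low-diastolic limit elsewhere, nothing else supplies the missing criterion. A programmer who follows the text produces a table with no low-diastolic count. One who corrects it silently departs from the plan.

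What is at stake is one row of a descriptive safety table. Safety is a primary objective in every part of the trial, and diastolic pressure is measured before, during and after each infusion (Protocol 9.2.10), so the data for the row will exist. The printed table would also contain a systolic ≤50 mmHg row that is likely to be empty or nearly so. A reader skimming the table could take that row as covering hypotension more fully than it does.

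**Working it through.** The plan states no figure to reproduce, and no sample size or error rate is involved. The check is a reading of the six rows in SAP 3.6.4.

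**Step 1: tally the rows by parameter and direction.**

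| Row | Parameter as written | Limit | Change from baseline | Direction |
|---|---|---|---|---|
| 1 | Systolic | ≥160 mmHg | +20 mmHg or more | high |
| 2 | Systolic | ≤90 mmHg | −20 mmHg or more | low |
| 3 | Diastolic | ≥100 mmHg | +15 mmHg or more | high |
| 4 | Systolic | ≤50 mmHg | −15 mmHg or more | low |
| 5 | Heart rate | ≥120 bpm | +15 bpm or more | high |
| 6 | Heart rate | ≤50 bpm | −15 bpm or more | low |

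As written, systolic has three rows (one high, two low), diastolic has one (high only) and heart rate has two. With row 4 read as diastolic, there are 3 parameters × 2 directions = 6 rows and no gap.

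**Step 2: compare the change criteria.** Rows 1 and 2 both use 20 mmHg. Row 3 uses 15 mmHg, and so does row 4. Row 4 therefore matches the diastolic row above it and differs from both of the other systolic rows.

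**Step 3: ask what row 4 adds if it is taken literally.** Let S be the post-baseline systolic value, B the baseline value and d = B − S the fall.

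- Row 4 requires S ≤ 50 and d ≥ 15.
- Row 2 requires S ≤ 90 and d ≥ 20.
- S ≤ 50 implies S ≤ 90, so a reading that meets row 4 misses row 2 only if 15 ≤ d < 20.
- In that case B = S + d < 50 + 20 = 70 mmHg.

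So literal row 4 adds only patients whose systolic pressure was already below 70 mmHg at baseline, which is under the SAP's own low-systolic limit of 90 mmHg. The row is almost wholly redundant.

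**Step 4: work an illustrative case.** Take a diastolic fall from 70 to 48 mmHg, with systolic pressure and heart rate outside their limits.

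- The fall is 70 − 48 = 22 mmHg, which is at least 15, and 48 ≤ 50. The reading meets row 4 if that row is diastolic.
- As written, rows 1, 2 and 4 look at systolic pressure, row 3 needs a diastolic value of at least 100 mmHg, and rows 5 and 6 look at heart rate. None is met.

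**Result.** The number of criteria based on low diastolic pressure is 0 as written and 1 after the correction.

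**The case against.** The strongest reply concedes the slip and disputes its weight. Most of that reply stands.

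- **Diastolic data are not lost.** A reader might infer that low diastolic pressure goes unreported. The section does not support that: the minimum post-baseline value, its change from baseline and the full patient listing all remain. What is missing is the count and proportion.
- **Some affected patients are still counted.** A reader might infer that every patient with a diastolic value of 50 mmHg or less drops out of the table. A patient whose systolic pressure also falls by at least 20 mmHg to 90 mmHg or below is counted in row 2. Only those who meet no other criterion are absent.
- **No false zero is printed.** Low diastolic pressure would be absent from the table, not shown as zero. The systolic ≤50 mmHg row would be correct for its label.
- **The link to infusion reactions is indirect.** Protocol 5.3.2 reports Grade 2 infusion-related reactions as the most frequent treatment-related events, but for Part A only, and it does not mention hypotension. Such events are captured mainly in the adverse-event tables of SAP 3.6.2, where Grade 3 or 4 infusion reactions are also events of special interest.
- **The data set is small and the table is secondary.** Protocol 5.3.2 gives 26 patients exposed in Part A. SAP section 6 gives 5 enrolled in Part A-2 and 5 + 5 + 10 = 20 in Part B. If all those enrolled were dosed, that is 26 + 5 + 20 = 51 patients, so the listing can be read in full. No hypothesis tests are planned (SAP 3.1.5), and Protocol 10.6.9 makes such summaries optional.
- **The programming is not visible.** SAP section 7 places the detailed specifications in a separate document, and SAP 5.3 has comments on the pre-final output resolved before the final analysis. The slip may be caught there.

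One further defence is that row 4 is a deliberate second tier for extreme systolic hypotension. That does not hold up well: a more extreme limit would then be paired with a smaller required fall than row 2, and there would still be no low-diastolic row.

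These points limit the consequence. They do not make the row right. The SAP says it will present numbers and proportions, and group minima and a listing do not supply them.

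**Conclusion.** The point holds as an error in a stated analysis rule with a limited consequence. Row 4 of the thresholds in SAP 3.6.4 names the wrong parameter. Programmed as written, it yields two low-systolic criteria, one nearly redundant, and no count or proportion of patients with low diastolic pressure.

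That diastolic was meant is an inference. It rests on the row's position, the shared 15 mmHg change, the near-redundancy of the literal reading and the completeness of the list once corrected. Together these make it a strong inference, but the sponsor should confirm it. How many patients are affected cannot be stated, because the documents give no vital-sign results and the programming specification is not available.

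The documents do not support any larger conclusion, such as hypotension going unseen in this trial or safety decisions being affected. Diastolic readings appear in two other displays. No endpoint, dose-limiting-toxicity rule or stopping rule uses this table, and efficacy is untouched.

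**What to change.** Confirm the intended parameter with the SAP's authors. Then replace systolic by diastolic in the row with the 50 mmHg limit and the 15 mmHg decrease, leaving the numbers as they are, and check that the vital-signs table specification and shell agree.

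SAP section 1 says the plan is finalized before database lock and that later deviations are documented in the clinical study report. If lock has already passed, program the corrected row and record the change there.

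The cost is one word in the SAP and a check of one table. No new data are needed.

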3.6.5 Electrocardiograms

All ECG data will be listed by patient.

3.6.6 Performance Status

A shift table from baseline ECOG performance status to worst post-baseline status will be presented.

All ECOG performance status data will be listed by subject.

3.6.7 Other Safety Assessments

The following safety assessments will be listed by patient:

- All clinically significant (by investigator assessment) physical examinations,
- All clinically significant (by investigator assessment) neurological examinations,
- All positive COVID-19 tests,

4 SAFETY MONITORING COMMITTEE AND DATA MONITORING COMMITTEE

A Safety Monitoring Committee (SMC) monitored and reviewed accumulating data to detect potential risks to enrolled patients. The SMC evaluated delayed DLTs, reviewed ad-hoc safety issues, and supported the Sponsor in MTD determination. They were also planned to support the interim futility decisions for the Part B cohorts. The SMC consisted of an independent (i.e. not an investigator in the study) Chair and site investigators. Full details on SMC membership responsibilities are found in the SMC charter.

The SMC together with the Sponsor selected the dose levels and dosing intervals for Part B of the trial. A Data Monitoring Committee (DMC) was planned to review the accumulating clinical activity, PK/PD, ADA, and RO data, but was not needed due to early closure of the trial.

5 ANALYSIS TIMING

5.1 Interim Analysis

No interim analysis will be provided.

5.2 Pre-Final Analysis

After the database is locked, the pre-final analysis will be generated. Pre-final TFLs will be provided approximately 4 weeks after database lock.

5.3 Final Analysis

After all comments on the pre-final analysis have been resolved and the study database is declared final, the final analysis will be generated. Final TFLs will be provided approximately 1 week after the study database is declared final. If there were no changes to the pre-final analysis or the study database, the pre-final TFLs may be considered final. In addition to TFLs, SDTM data and ADaM data along with associated files will be provided. Associated files may include annotated case report forms (CRFs), SDTM specifications, SDTM programs, ADaM specifications, ADaM programs, TFL programs, and CDISC Define packages for both SDTM and ADaM data.

6 CHANGES FROM PROTOCOL-SPECIFIED STATISTICAL ANALYSIS

Only limited patients were enrolled onto the study under Cohort B1 (5 patients), Cohort B7 (5 patients) and Cohort B8 (10 patients) in Part B. Cohort A-2 only enrolled 5 patients. There are no patients enrolled under Cohort B2, Cohort B3, Cohort B4, Cohort B5 and Cohort B6 in Part B. Therefore, due to the limited data, only related TFLs will be generated and no interim analyses were performed.

7 PROGRAMMING SPECIFICATIONS

Analyses will be performed using SAS® version 9.3 or higher. Phoenix WinNonlin version 8.1 or higher will be used in the determination of the PK terminal phase and the calculation of PK parameters. All the PK parameters will also be calculated via SAS® and verified with the Phoenix WinNonlin results. Detailed Programming Specifications for the final analysis will be provided in a separate document.

APPENDIX A: PARTIAL DATE CONVENTIONS

Table 2 Algorithm for Treatment-Emergent Adverse Events

AE Start Date	AE Stop Date	Action
Known	Known	If start date < study drug start date, then not TEAE If start date \geq study drug start date, then TEAE
	Partial	If start date < study drug start date, then not TEAE If start date \geq study drug start date, then TEAE
	Missing or Unknown	If start date < study drug start date, then not TEAE If start date \geq study drug start date, then TEAE
Partial, but the known date components show that it cannot be on or after study drug start date	Known	Not TEAE
	Partial	Not TEAE
	Missing or Unknown	Not TEAE
Partial, could be on or after study drug start date	Known	If stop date < study drug start date, then not TEAE If stop date \geq study drug start date, then TEAE
	Partial	Impute stop date as latest possible date (i.e., last day of month if day is unknown or 31-Dec if day and month are unknown), then: If stop date < study drug start date, then not TEAE If stop date \geq study drug start date, then TEAE
	Missing or Unknown	Assumed TEAE
Missing or Unknown	Known	If stop date < study drug start date, then not TEAE If stop date \geq study drug start date, then TEAE
	Partial	Impute stop date as latest possible date (i.e., last day of month if day is unknown or 31st December if day and month are unknown), then: If stop date < study drug start date, then not TEAE If stop date \geq study drug start date, then TEAE
	Missing or Unknown	Assumed TEAE

TEAE = treatment-emergent AE

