- d. In the case that an infusion cannot be administered at a scheduled visit, it has to be administered as soon as possible. If the delay is between 1 and 7 days, the procedures at the original scheduled visit should be performed. If the delay is more than 7 days, the procedures at the next visit should be performed, and subsequent visits will follow every 2 weeks (the infusion at the original scheduled visit will be considered a missed dose). Patients with infusion delays >35 days (i.e., 2 missed doses + 7 days) should normally discontinue treatment and enter the Follow-up period with the exception of delays related to prophylactic vaccinations in special cases needed after specific consultation and agreement between the Investigator, and the Medical Monitor or in settings where benefit/risk may justify continued study therapy (e.g., patient deriving clinical benefit who requires prolonged steroid taper for management of non-DLT irAEs; again upon agreement with the Medical Monitor).
- e. Treatment and imaging/tumor assessments will continue until discontinuation criteria have been met.
- f. ICF and HIPAA – or any locally applicable – authorization are to be provided before initiation of any Screening assessments and may be obtained before Day 28.
- g. To include collection of prior medication and prior/concurrent medical conditions. Also to include collecting prior local test results on tumor genetic alterations such as MSI-H, dMMR, *BRCA1*, *Kras*, PD-L1 status, TMB, etc. (if available).
- h. AEs occurring after signing informed consent/HIPAA authorization, but before study drug administration are to be recorded as AEs (though non-treatment-emergent).
- i. Hepatitis B surface antigen (HBVs Ag), Anti-Hepatitis B surface antibody (HBVs Ab), Anti-Hepatitis B core antibody (HBVc Ab), a Hepatitis B panel, and anti-hepatitis C antibody (HCV ab) (with reflex viral load assessment by quantitative polymerase chain reaction (PCR) hepatitis C RNA if antibody test is positive) testing. To be done by local site laboratory or its contract laboratory.
- j. CD4 T-cell count should only be performed if a patient is HIV positive at Screening.

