9.2.1.5 Treatment-Emergent Adverse Event

TEAEs are defined as any AE occurring or worsening on or after the first dose of study drug.

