9.2.4 Recording of AEs and SAEs

When an AE/SAE occurs, it is the responsibility of the Investigator to review all documentation (e.g., hospital progress notes, laboratory reports, and diagnostics reports) related to the event. The Investigator will then record all relevant AE/SAE information in the eCRF. It is not acceptable for the Investigator to send photocopies of the participant's medical records in lieu of completion of the AE/SAE eCRF page. There may be instances when copies of medical records for certain cases are requested. In this case, all participant identifiers, except for the participant number, will be redacted on the copies of the medical records before submission. The Investigator will attempt to establish a diagnosis of the event based on signs, symptoms, and/or other clinical information. Whenever possible, the diagnosis (not the individual signs/symptoms) will be documented as the AE/SAE.

The following variables will be recorded for each AE: verbatim/AE description and date for AE start and stop, severity (refer to [Section 9.2.4.1](#)), seriousness ([Section 9.2.1.4](#)), causality rating ([Section 9.2.4.2](#)), whether or not the AE caused the participant to discontinue ([Section 9.2.4.3](#)), any other action ([Section 9.2.4.4](#)), and the outcome ([Section 9.2.4.5](#)). A new AE must be recorded if the severity of the AE changes.

Should an SAE have an outcome of death, the report should contain a comment regarding the co-involvement of progression of disease, if appropriate, and should assign main and contributory causes of death.

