Possibly	A clinical event, including laboratory test abnormality, with a reasonable time sequence to drug administration but which could also be explained by concurrent disease or other drugs or chemicals. Information on drug withdrawal may be lacking or unclear.	
 1. It follows a reasonable temporal sequence from study drug administration. 2. It could also be explained by participant's concurrent disease, environmental factors, medical history and other concomitant drugs or chemicals (including food-drug interactions). 3. There is no information or uncertainty with regard to what has happened after stopping the drug.
At least possibly	
A TEAE is an AE with onset after administration of first study dose and is independent of any assessment of causality.
 
Any TEAE that is considered at least possibly related to study drug is considered a TRAE.
	
Probably	
A clinical event, including laboratory test abnormality, with a reasonable time sequence to drug administration, unlikely to be attributed to concurrent disease or other drugs or chemicals, and which follows a clinically reasonable response on withdrawal (de-challenge). Re-challenge information is not required to fulfill this definition.
	
 1. It follows a reasonable temporal sequence from study drug administration. 2. It could not be readily explained (unlikely) by the participant's concurrent disease, environmental factors, medical history and other concomitant drugs or chemicals including food-drug interactions. 3. It disappears or decreases in severity on cessation or reduction in dose or on administration of a specific antagonist wherever possible. There are important exceptions when an AE does not disappear upon discontinuation of the drug, yet drug-relatedness clearly exists. 4. No re-challenge information is available or possible.

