3.6.2 Adverse Events (AEs)

AEs will be captured from signing informed consent/HIPAA authorization, through 70 days after the last dose of study drug, as specified in section 9.2.4 of the protocol. Beyond 70 days from the last dose of study drug, only study treatment-related SAEs or late-occurring irAEs should be reported. All AEs will be coded to system organ class and preferred term using MedDRA version 25.0 or later.

Treatment-emergent adverse events (TEAEs) are defined as AEs that occur or worsen on or after the first dose of study drug.

Adverse events of special interest (AESIs) are defined in section 9.2.1.6 of the protocol as:

- Elevations of ALT/AST that are >3-fold above baseline,
- AEs falling under the system order class (SOC) of hepatobiliary disorders (i.e., to cover any potential liver toxicity) Grade 3 or higher,
- SOC of immune system disorders (i.e., to cover cytokine release syndrome and irAEs) Grade 3 or higher,
- Any AE of CTCAE V5.0 Grade 3 or higher,
- Any CTCAE V5.0 Grade 3 or 4 infusion reaction whether or not the event is a DLT or delayed DLT,
- Any AE considered by the Investigator to represent a DLT or delayed DLT.

AESI's will be identified by the investigator and recorded in the eCRF.

Immune-related AEs (irAEs) will be identified by the investigator and recorded in the eCRF.

An overview of AEs will be provided including counts and percentages of subjects (and event counts) with the following types of AEs:

- Any TEAEs (overall, by maximum severity, and grade ≥ 3)
- Any NM21-1480-related TEAEs (overall, by maximum severity, and and grade ≥ 3)
- Any TEAEs of special interest (overall, by maximum severity, and grade ≥ 3)
- Treatment-emergent irAEs
- Any serious AEs (SAEs)
- Any treatment-emergent serious AEs (TESAEs)
- Any NM21-1480-related TESAEs
- Any TEAEs leading to temporary or permanent discontinuation of NM21-1480
- Any AEs leading to death

The number and percentage of patients with AEs will be summarized by system organ class (SOC) and preferred term (PT) for the following types of AEs:

- TEAEs
- Grade ≥ 3 TEAEs

- NM21-1480-related TEAEs
- Grade ≥ 3 NM21-1480-related TEAEs
- TEAEs of special interest
- Treatment-emergent irAEs
- TESAEs
- NM21-1480-related TESAEs

The number and percentage of patients with AEs will be summarized by SOC, PT, and highest CTCAE grade for the following types of AEs:

- TEAEs
- NM21-1480-related TEAEs

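### SAP Table 2 decides treatment-emergence by record start date alone, so a pre-dose AE that only improves on drug counts as a TEAE, and overview event counts measure grade steps

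*SAP*

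**What the plan says.** Protocol 9.2.4 tells sites how to record a change in severity: "A new AE must be recorded if the severity of the AE changes". It gives no direction, so a fall in grade triggers a new record as much as a rise. Recording starts at consent. Protocol 7.1.6 (Table 7-1, footnote h) has events between consent and first dose entered as AEs and treats them as not treatment-emergent.

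The definition appears in two main places. SAP 3.6.2: "Treatment-emergent adverse events (TEAEs) are defined as AEs that occur or worsen on or after the first dose of study drug". Protocol 9.2.1.5: "TEAEs are defined as any AE occurring or worsening on or after the first dose of study drug". Protocol Table 9-1 (section 9.2.4.2) has a shorter wording that leaves out worsening: "A TEAE is an AE with onset after administration of first study dose and is independent of any assessment of causality".

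The working rule is SAP Appendix A, Table 2. For a known start date before study drug start it says "If start date < study drug start date, then not TEAE"; for a known start date on or after study drug start, the record is a TEAE. Severity plays no part in any row.

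On counting, SAP 3.6.2 says: "An overview of AEs will be provided including counts and percentages of subjects (and event counts) with the following types of AEs". The tables by system organ class and preferred term, and those by highest grade, count patients. Neither document links several records of one event.

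**The concern.** Each rule is reasonable alone. Together they conflict. An event that began in screening and eases after Day 1 has neither arisen nor worsened on drug, yet its second record starts after first dose and Table 2 makes it a TEAE.

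Incidence and severity of TEAEs is a primary endpoint in Parts A, A-2 and B. A falsely emergent record enters the patient-level tables. If the improved grade is still 3 or higher, it enters the Grade ≥3 table and meets one of the criteria for an event of special interest. If causality is missing, SAP 3.1.7 makes it drug-related.

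The second issue is the unit of the event counts. With one record per grade, an event that rises and falls is counted several times in the overview.

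**Working it through.** The plan states no figure on this point, so there is none to reproduce. The check applies both rules to hypothetical histories.

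**Inputs**
- One record per grade: Protocol 9.2.4.
- Table 2 rule, per record: TEAE if record start ≥ Day 1 (SAP Appendix A).
- Definition, per event: TEAE if the event first starts on or after Day 1, or its highest post-dose grade exceeds its last pre-dose grade (SAP 3.6.2, Protocol 9.2.1.5).
- Enrolled: B1 5, B7 5, B8 10, A-2 5 (SAP section 6).
- Assumption: the new record starts on the day the grade changes. The protocol does not say so for AEs. Protocol 9.2.6 dates an SAE from the day the event becomes serious, which points the same way.

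**Step 1: the two rules side by side**

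| Hypothetical event | Table 2: TEAE records | of which Grade ≥3 | Table 2: patients | Definition: TEAEs |
|---|---|---|---|---|
| A. Pre-dose Grade 2, falls to 1 on Day 5 | 1 | 0 | 1 | 0 |
| B. Pre-dose Grade 1, rises to 2 on Day 5 | 1 | 0 | 1 | 1 |
| C. Onset Day 10, Grades 1, 2, 3, 2, 1 | 5 | 1 | 1 | 1 |
| D. Pre-dose Grade 4, falls to 3 on Day 3, then 2 on Day 6 | 2 | 1 | 1 | 0 |
| E. Pre-dose Grade 1, unchanged | 0 | 0 | 0 | 0 |

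The records sum to 1 + 1 + 5 + 2 + 0 = 9, against 0 + 1 + 1 + 0 + 0 = 2 events under the definition. These totals show the mechanism and estimate nothing. A and D are wrong at patient level. C is wrong only in the event count.

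**Step 2: patient-level size.** One falsely emergent patient adds 1/n to a term's incidence: 1/5 = 20 points in B1, B7 or A-2, and 1/10 = 10 points in B8. In the Part B total, n = 5 + 5 + 10 = 20, so 1/20 = 5 points. This takes all enrolled patients as dosed, and requires that the patient has no genuine TEAE of that term.

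**Step 3: event counts.** Records per event = grade changes + 1. Event C has 4 changes, so 5 records. If a share s of on-treatment events goes one grade up and one down, records per event average 1 + 2s and the excess is 2s: 0% at s = 0, 40% at s = 0.2, 80% at s = 0.4. The documents give no value for s.

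**Step 4: the other dating convention.** Suppose each new record kept the original onset date. A and D would then be classed correctly. In B, however, both records would start before Day 1, so Table 2 gives 0 TEAEs where the definition gives 1. C would still give 5 records. Table 2 departs from the definition under either convention.

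**The case against.** The strongest reply is that the definition governs and already excludes improvements. SAP 3.1.7 introduces Table 2 for missing and partial dates, and the appendix title says the same. That has some force, but the table's first block covers fully known dates, and it is the only operational rule the SAP gives. The SAP does not say which text prevails.

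Second, the pre-dose route is narrow. It needs an AE that starts after consent, is still present at Day 1, and then improves without exceeding its pre-dose grade. Findings at screening and pre-treatment examinations go to medical history (Protocol 7.1.6 table notes and 9.2.9), and ordinary fluctuation of pre-existing conditions is not an AE (9.2.1.3). This stands. It leaves some cases: Cohort B8, for example, has a mandatory screening biopsy, and a procedural event could ease after Day 1.

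Third, a new record on improvement is an inference, since Protocol 9.2.4.5 has a resolving outcome that could capture it. The wording of 9.2.4 still covers any change.

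Fourth, SAP section 7 puts programming specifications in a separate document, which may link records. That cannot be checked here, and the derivation of a primary endpoint belongs in the SAP.

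A reader might also infer that record splitting inflates TEAE incidence or severity generally. The documents do not support that: the term and highest-grade tables count each patient once. Nor do they support any specific inflation of the event counts, because the share in Step 3 has no source.

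**Conclusion.** The point holds within limits. For known dates, Table 2 contradicts the definition in SAP 3.6.2 and Protocol 9.2.1.5, because it compares dates and never grades. A pre-dose AE that only improves after first dose is counted as a TEAE, including at patient level; if sites carry the original onset date forward, a pre-dose AE that worsens is missed instead. The event counts in the overview, and only those among the summary tables, measure grade steps; the listings will show the same split records.

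The effect is 10 to 20 points for a single term in cohorts of 10 to 5 patients, for one affected patient without a genuine TEAE of that term. The number of such patients and the excess in event counts cannot be computed from the documents. The SAP plans no hypothesis tests and lists all AE data by patient, so no formal inference is affected. It should still be corrected, because a stated rule for a primary endpoint gives a wrong classification.

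**What to change.** Add to SAP 3.6.2 and Table 2:

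1. A record that continues a pre-dose AE is treatment-emergent only if its grade exceeds the last pre-dose grade.
2. Contiguous records of the same event in a patient are linked, for example where the next record starts on the previous stop date or the day after.
3. Overview event counts use linked events, each graded by its maximum post-dose grade, so that a higher pre-dose grade is not attributed to treatment.
4. Causality of a linked event is the most conservative assessment among its records.
5. Where partial or missing dates prevent linkage, records stay unlinked and the current Table 2 rule applies.

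The text should also state which date starts a record opened for a severity change, and how linkage treats a start date reset because the event became serious (Protocol 9.2.6).

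The cost is a few sentences in the SAP and a linkage derivation with its checks. No new data are needed.
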